#### **9.2.1.1. Adverse Device Effects**

Any AE believed to be related to an issue with the investigational device (AI) or to the use of the study device (PFS) is considered an adverse device event. These events must be clearly indicated as such in the eCRF, and reported to the sponsor. A PC should also be reported.

For the purpose of this protocol, “unanticipated” adverse device effect means any serious adverse event alleged to be associated or related to the device, and which has been confirmed as such by the sponsor. The SAE relatedness must be clearly indicated as such in the eCRF, and reported to the sponsor within 24 hours of site knowledge of the event. A PC should also be reported.

#### **9.2.1.2. Adverse Events of Special Interest**

The following AEs of special interest will be used to determine the safety and tolerability of LY3074828 injections administered by either investigational PFS or investigational AI in this clinical study.

Adverse events of special interest for LY3074828 are:

- infection
- injection-site reactions
- allergic/hypersensitivity reactions

If infections, injection-site reactions, or allergic/hypersensitivity reactions are reported, sites will provide details on these events as instructed on the eCRF. Investigators will also educate subjects about the symptoms of allergic/hypersensitivity reactions and will provide instructions on dealing with these reactions. A blood sample will be collected when possible for any subject who experiences an AE of allergic/hypersensitivity reaction during the study.

#### **9.2.1.3. Suspected Unexpected Serious Adverse Reactions**

Suspected unexpected serious adverse reactions (SUSARs) are serious events that are not listed in the IB and that the investigator identifies as related to IP or procedure. Lilly has procedures that will be followed for the recording and expedited reporting of SUSARs that are consistent with global regulations and the associated detailed guidances.

#### **9.2.1.4. Adverse Event Monitoring with a Systematic Questionnaire**

Before administering the SF-MPQ, study site personnel will question the subject about any change in the preexisting condition(s) and the occurrence and nature of any AEs.

Injection-site assessment at the scheduled protocol time points will not be double reported in the AE form, but will be captured in the eCRF.

Only *serious* AEs elicited through the SF-MPQ are to be recorded as AEs via electronic data entry and reported to Lilly or its designee within 24 hours as SAEs.

Unsolicited AEs (e.g., headache, redness reported by subjects during the follow-up period) will be reported in the AE form.

### **9.2.2. Complaint Handling**

Lilly collects PCs on IPs and drug delivery systems used in clinical trials in order to ensure the safety of study participants, monitor quality, and to facilitate process and product improvements.

Subjects should be instructed to contact the investigator as soon as possible if he or she has a complaint or problem with the IP or drug delivery system so that the situation can be assessed. A PFS or AI that is associated with a product quality issue or complaint must be returned to Lilly.

The investigator or his/her designee is responsible for handling the following aspects of the PC process in accordance with the instructions provided for this study:

- recording a complete description of the PC reported and any associated AEs using the study-specific complaint forms provided for this purpose,
- faxing the completed Product Complaint Form within 24 hours to Lilly or its designee.

If the investigator is asked to return the product for investigation, he/she will return a copy of the Product Complaint Form with the product.

### **9.3. Treatment of Overdose**

For the purposes of this study, an overdose of LY3074828 is considered any dose higher than the dose assigned through randomization.

There is no specific antidote for LY3074828. In the event of an overdose, the subject should receive appropriate supportive care and any AEs should be documented.

Refer to the study drug IB for further details.

## **9.4. Safety**

### **9.4.1. Laboratory Tests**

For each subject, clinical laboratory tests detailed in [Appendix 2](#) should be conducted according to the Schedule of Activities (Section 2).

Lilly or its designee will provide the investigator with the results of laboratory tests analyzed by a central vendor, if a central vendor is used for the study.

### **9.4.2. Vital Signs**

For each subject, vital sign measurements (blood pressure, pulse rate, and temperature) should be conducted according to the Schedule of Activities (Section 2). Additional vital signs may be measured during the study if warranted.

Blood pressure and pulse rate should be measured after at least 5 minutes supine.

Unscheduled orthostatic vital signs should be assessed where considered appropriate by the investigator. If orthostatic measurements are required, subjects should be supine for at least 5 minutes and stand for at least 3 minutes. If the subject feels unable to stand, supine vital signs only will be recorded.

### **9.4.3. Electrocardiograms**

For each subject, a single 12-lead digital ECG will be collected according to the Schedule of Activities (Section 2). Electrocardiograms must be recorded before collecting any blood for safety or PK tests. Subjects must be supine for at least 5 minutes before ECG collection and remain supine but awake during ECG collection. Electrocardiograms may be obtained at additional times, when deemed clinically necessary by the investigator. All ECGs recorded should be stored at the investigational site.

Electrocardiograms will be interpreted by the investigator or qualified designee at the site as soon after the time of ECG collection as possible, and ideally while the subject is still present, to determine whether the subject meets entry criteria at the relevant visit(s) and for immediate subject management, should any clinically relevant findings be identified.

If a clinically significant finding is identified (including, but not limited to, changes in QT/corrected QT interval from baseline) after enrollment, the investigator will determine if the subject can continue in the study. The investigator, or qualified designee, is responsible for determining if any change in subject management is needed, and must document his/her review of the ECG printed at the time of collection.

Any clinically significant findings from ECGs that result in a diagnosis and that occur after the subject receives the first dose of the IP should be reported to Lilly, or its designee, as an AE via eCRF.

### **9.4.4. Other Tests**

#### **9.4.4.1. Tuberculosis Testing**

Subjects will be tested as indicated in the Schedule of Activities (Section 2) for evidence of active or latent TB using the QuantiFERON-TB Gold test. If the test is indeterminate, 1 retest is allowed. If the retest is indeterminate, the subject will be excluded from the study.

Subjects who have had household contact with a person with active TB must be excluded unless appropriate and documented prophylaxis treatment for TB has been completed.

Subjects with any history of active TB are excluded from the study, regardless of previous or current TB treatments.

#### **9.4.4.2. Injection Instructions**

Prior to the PFS or AI injection, the investigator or his/her designee will prepare the subject's skin. The injections will be given according to the instructions provided by the sponsor.

Pre-filled syringe injections into the abdomen will be administered by investigative site staff. All subjects will receive training on how to use the AI to self-administer into the abdomen. The investigator or his/her designee will answer any questions the subject may have and will demonstrate the steps required for injection according to the IFU. Subjects will be monitored while using the AI to ensure successful self-injections. Investigative site staff who observe the subject's self-injection with the AI will fill out the AI Use Assessment Questionnaire. All study injection sites will be marked using a template for size and with a surgical marker in order to identify study injection sites for later assessments.

#### **9.4.4.3. Injection Speed Assessments and Video Recording**

Injection duration will be measured by a calibrated stopwatch by qualified trained study staff. For Part A, the duration of injection for the PFSs will be defined as the time between when the plunger rod is pressed down and when all of the LY3074828 solution is injected. For Part B, the duration of injection for the AIs will be defined as the time between the first audible click after the injection button is pressed and the last audible click, which indicates that the needle has retracted and the injection is complete.

For Part B, a video recorder will be used to record the AI injection site and the device as it is being used. The video recordings may be examined to explore device functionality. The subject's face, voice, or identifiable markings will not be video recorded. The video recording will be identified by the subject number. The video data will be managed by the sponsor and securely stored electronically in the sponsor's network. Further analysis of the video recordings may be performed by qualified sponsor personnel after completion of the study.

#### **9.4.4.4. Injection-site Assessments**

While the SF-MPQ will be administered to capture data for pain on injection, other injection-site reactions will be captured in the subjects' eCRF as AEs (including erythema, induration, categorical pain, pruritus, and edema).

#### **9.4.4.5. Bleeding Assessment**

All injection sites will be observed at the times indicated in the Schedule of Activities (Section 2) by the investigator or designee, and the presence of visible bleeding will be recorded on the eCRF. A bandage may be placed on the injection site after assessment.

#### **9.4.4.6. Injection-site Pain**

##### **9.4.4.6.1. Short Form McGill Pain Questionnaire**

Acute pain from SC injection will be assessed using the 15-item short form of the SF-MPQ (Melzack 1987) modified to meet the purpose of the study at times specified in the Schedule of Activities (Section 2).

As part of the SF-MPQ, pain measurements will be quantified using the 100-mm validated VAS for all subjects, whether or not they report injection pain. The VAS is a well-validated tool (Williamson and Hoggart 2005) to assess injection-site pain; it is presented as a 100-mm line

anchored by verbal descriptors, usually “no pain” and “worst possible pain.” The subject will be asked to rate any pain on a scale of 0 to 100 mm on the line immediately (approximately within 5 minutes) following the start of the injection and at the time points listed in the Schedule of Activities (Section 2).

For 1-mL PFS, assessments are to be completed on the first of the 2 injections only.

#### **9.4.5. Safety Monitoring**

The Lilly CP or CRP/scientist will monitor safety data throughout the course of the study.

Lilly will review SAEs within time frames mandated by company procedures. The Lilly CP or CRP will periodically review the following data:

- trends in safety data
- laboratory analytes
- AEs, including monitoring of incidence of any nature of any infections, and injection-site reactions
- PCs

When appropriate, the Lilly CP or CRP will consult with the functionally independent Global Patient Safety (GPS) therapeutic area physician, GPS device physician, or GPS clinical research scientist.

##### **9.4.5.1. Hepatic Safety**

If a study subject experiences elevated alanine aminotransferase (ALT)  $\geq 3 \times$  upper limit of normal (ULN), alkaline phosphatase (ALP)  $\geq 2 \times$  ULN, or elevated total bilirubin (TBL)  $\geq 2 \times$  ULN, liver tests (Appendix 4) should be repeated within 3 to 5 days including ALT, aspartate aminotransferase, ALP, TBL, direct bilirubin, gamma-glutamyl transferase, and creatine phosphokinase to confirm the abnormality and to determine if it is increasing or decreasing. If the abnormality persists or worsens, clinical and laboratory monitoring should be initiated by the investigator based on consultation with the Lilly CP or CRP. Monitoring should continue until levels normalize and/or are returning to approximate baseline levels.

Additional safety data should be collected if 1 or more of the following conditions occur:

- elevation of serum ALT to  $\geq 5 \times$  ULN on 2 or more consecutive blood tests
- elevated serum TBL to  $\geq 2 \times$  ULN (except for cases of known Gilbert’s syndrome)
- elevation of serum ALP to  $\geq 2 \times$  ULN on 2 or more consecutive blood tests
- hepatic event considered to be an SAE

##### **9.4.5.2. Monitoring of Hypersensitivity Reactions**

There is a risk of systemic hypersensitivity reactions with any biological agent, including acute anaphylaxis and delayed hypersensitivities to LY3074828. Symptoms and signs that may occur as part of these hypersensitivity reactions include, but are not limited to: fever, chills, joint and

muscle pain, rash, itching, urticaria, dizziness, headache, throat irritation, and shortness of breath. Less commonly, life-threatening anaphylactic reactions may occur, which may include vascular collapse and/or respiratory compromise.

All subjects will be closely monitored for signs and symptoms of hypersensitivity reactions following administration of the study drug, and appropriate medical care should be provided. Hypersensitivity reactions will be evaluated by examination of TEAEs and SAEs, and through the use of a follow-up form which will be completed by the investigator. Potential hypersensitivity events will be evaluated by a Lilly CRP based on accepted criteria (Sampson et al. 2006).

## **9.5. Pharmacokinetics**

At the visits and times specified in the Schedule of Activities (Section 2), venous blood samples of approximately 2 mL each will be collected to determine the serum concentrations of LY3074828 for Parts A and B. A maximum of 3 samples may be collected at additional time points during the study if warranted and agreed upon between both the investigator and sponsor. Instructions for the collection and handling of blood samples will be provided by the sponsor. The actual date and time (24-hour clock time) of each sampling will be recorded.

Pharmacokinetic samples will be collected in both Part A and Part B; however, PK statistical analyses will only be performed for Part A. Samples from Part B will be stored and will only be sent for bioanalysis at a later date based on immunogenicity or safety results from Part B of the study.

### **9.5.1. Bioanalysis**

Samples will be analyzed at a laboratory approved by the sponsor and stored at a facility designated by the sponsor. Concentrations of LY3074828 will be assayed using a validated enzyme-linked immunosorbent assay.

Bioanalytical samples collected to measure IP concentrations will be retained for a maximum of 1 year following last subject visit for the study.

## **9.6. Pharmacodynamics**

### **9.6.1. Immunogenicity Assessments**

Blood samples for immunogenicity testing will be collected to determine antibody production against LY3074828, as specified in the Schedule of Activities (Section 2) for Parts A and B. Additional samples may be collected if there is a possibility that an AE is immunologically mediated. If additional immunogenicity testing samples are taken, matching PK sample collections will also be required. Immunogenicity will be assessed by a validated assay designed to detect ADAs in the presence of the IP. Antibodies may be further characterized and/or evaluated for their ability to neutralize the activity of the IP.

A risk-based approach will be used to monitor subjects who develop TE-ADAs during and following treatment with LY3074828. Treatment-emergent ADAs are defined as either a 2-fold

increase in titer (i.e., 1:20) above the minimum required dilution (1:10) if no ADAs were detected at baseline (predose), or a 4-fold or greater increase in titer over baseline for subjects that are ADA-positive at baseline. LY3074828 is a monoclonal antibody that binds to p19 of IL-23, and there is no unique/non-redundant endogenous protein counterpart, greatly minimizing the risk of cross-reactive ADA. Any potential risks of ADA development following this single-dose trial would be dependent on LY3074828 exposure outside of this clinical trial. The largest potential risk would be reaction upon subsequent drug exposure that could range in severity from mild local injection-site reactions to systemic anaphylaxis and/or systemic immune complex disease (Arthus-reaction). These potential risks would likely be associated with higher serum concentrations of ADA.

Given that the subjects have only a single exposure to LY3074828 in Part A, and only 2 doses over an approximately 24-hour period in Part B, any ADA response is anticipated to peak and then diminish due to lack of additional exposures. Subjects will have ADA sampling at baseline (predose) and Days 15, 29, 57, and 85 in Part A, and at baseline (predose) and Days 15, 43, and 86 in Part B. Subjects that are observed to have a titer greater than 1:1000, or non-decreasing titers that meet the definition of TE-ADA, will be requested to return every 3 months after the last sample to have follow-up ADA samples tested until the titer has returned to within 1 titer of their baseline or is clearly trending back to the baseline titer. The rationale for the definitions of both TE-ADA and return to baseline is based on the premise that a 1-titer change may result from expected assay variability.

Subjects followed for at least 1 year since last dose who have not returned to baseline, as defined above, will be assessed for safety concerns and, if no clinical sequelae are recognized by the clinical team, no further follow-up will be required. Subjects who have clinical sequelae that are considered potentially related to the presence of TE-ADA may also be asked to return for additional follow-up testing.

Samples will be retained for a maximum of 15 years after the last subject visit, or for a shorter period if local regulations and the institutional review board (IRB) allow, at a facility selected by the sponsor. The duration allows the sponsor to respond to future regulatory requests related to the IPs. Any samples remaining after 15 years will be destroyed.

## 9.7. Genetics

A blood sample will be collected for pharmacogenetic analysis as specified in the Schedule of Activities (Section 2), where local regulations allow.

Samples will not be used to conduct unspecified disease or population genetic research either now or in the future. Samples will be used to investigate variable exposure or response to LY3074828 and to investigate genetic variants thought to play a role in autoimmune and inflammatory diseases. Assessment of variable response may include evaluation of AEs or differences in efficacy.

All samples will be coded with the subject number. These samples and any data generated can be linked back to the subject only by the investigative site personnel.

Samples will be retained for a maximum of 15 years after the last subject visit, or for a shorter period if local regulations and/or IRB impose shorter time limits, for the study at a facility selected by Lilly or its designee. This retention period enables use of new technologies, response to regulatory questions, and investigation of variable response that may not be observed until later in the development of LY3074828 or after LY3074828 is commercially available.

Molecular technologies are expected to improve during the 15-year storage period and therefore cannot be specifically named. However, existing approaches include whole genome or exome sequencing, genome wide association studies, multiplex assays, and candidate gene studies. Regardless of technology utilized, data generated will be used only for the specific research scope described in this section.

## **9.8. Biomarkers**

This section is not applicable for this study.

## **9.9. Health Economics**

This section is not applicable for this study.

## 10. Statistical Considerations and Data Analysis

### 10.1. Sample Size Determination

A total of approximately 72 subjects (approximately 36 subjects per study Parts A and B) who fulfill the eligibility criteria will be randomized to 1 of 2 dosing regimen arms within their assigned study part, with 18 subjects randomized to each arm in order to ensure completion of 16 subjects in each. The estimated total variability (coefficient of variation) in AUC from time zero to infinity  $AUC(0-\infty)$ , AUC from time zero to time  $t$ , where  $t$  is the last sample with a measurable concentration ( $AUC[0-t_{last}]$ ), and maximum observed drug concentration ( $C_{max}$ ) was 49%, 49%, and 23%, respectively, in Study AMAA following a single SC dose of 120 mg LY3074828. The coefficient of variation of 49% was used for precision estimates and is assumed for all dosing regimen arms. A sample size of 64 subjects will provide a precision, in log scale, of approximately 0.28 for the geometric means ratio in  $AUC(0-\infty)$ ,  $AUC(0-t_{last})$ , and  $C_{max}$  of 1- to 2-mL solution formulation injection. That is, there is a 90% probability that the half-length of the 90% confidence interval (CI) of the geometric means ratio in log scale is not larger than 0.28. Subjects who are randomized but not administered treatment, or subjects that are administered treatment but do not have PK and ADA samples collected up to and including Day 57, may be replaced (maximum of 4 per arm per study part) to ensure that approximately 16 subjects from each dosing regimen arm complete the study.

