### **10.3.2. *Pharmacokinetic Analyses***

#### **10.3.2.1. *Pharmacokinetic Parameter Estimation***

For Part A, PK parameter estimates for LY3074828 will be calculated by standard noncompartmental methods of analysis.

The primary parameters for analysis will be AUC(0-∞), AUC(0-tlast), and Cmax for LY3074828. The secondary parameter for analysis will be the time to maximum observed drug concentration (tmax) of LY3074828. Other noncompartmental parameters, such as t1/2, apparent total body clearance of drug calculated after extra-vascular administration (CL/F), and apparent volume of distribution during the terminal phase after extra-vascular administration (Vz/F), may be reported.

For Part B, no PK parameters will be evaluated. Pharmacokinetic samples are collected only in conjunction with immunogenicity samples to provide serum concentrations of LY3074828 to aid in the interpretation of ADA data if needed. Samples will be stored and will only be sent for bioanalysis at a later date based on immunogenicity or safety results from Part B of the study.

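### The PK precision statement counts 64 subjects and claims 90% assurance for a half-length of 0.28; Part A's 32 completers give about 55% at the planning CV of 49%.

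*Protocol*

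**What the plan says.** Protocol 10.1 sets the size of the study: "A total of approximately 72 subjects (approximately 36 subjects per study Parts A and B"), "with 18 subjects randomized to each arm in order to ensure completion of 16 subjects in each". It takes variability from an earlier single-dose SC study, with CVs of 49% for both AUCs and 23% for Cmax, and then fixes one planning value: "The coefficient of variation of 49% was used for precision estimates and is assumed for all dosing regimen arms".

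The precision claim follows: "A sample size of 64 subjects will provide a precision, in log scale, of approximately 0.28" for the geometric mean ratio in AUC(0-∞), AUC(0-tlast) and Cmax. The next sentence defines that precision: "there is a 90% probability that the half-length of the 90% confidence interval (CI) of the geometric means ratio in log scale" does not exceed 0.28. SAP 7 makes the same claim.

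Elsewhere the protocol confines PK inference to Part A. Section 9.5 says "PK statistical analyses will only be performed for Part A", and section 10.3.2.1 says "For Part B, no PK parameters will be evaluated". Section 10.3.2.2 and SAP 9.3.2 specify a model on the log scale with dosing regimen arm as the only effect, comparing Test 1 with Reference and reporting the ratio with a 90% CI.

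**The concern.** Two parts of the claim conflict with the rest of the plan.

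- **The count.** 64 is 4 arms × 16 completers over Parts A and B, but only the two Part A arms (2 × 16 = 32) inform the ratio.
- **The probability.** A half-length assured with 90% probability must exceed the half-length at the planning SD, because the observed SD varies around its planning value. The stated 0.28 appears to contain no such allowance.

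This is the only sample-size justification in either document, and it concerns the primary PK endpoints. Part A is meant to bridge from two 1-mL injections to one 2-mL injection. Protocol 10.3.6 says the Part A data review will trigger manufacturing and control processes and inform Phase 3 dose selection. Anyone judging in advance whether Part A is large enough for those uses is given an assurance the design does not have.

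**Working it through.** **Inputs**

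- CV 49%, all arms and all three PK parameters (Protocol 10.1).
- Two-sided 90% CI, target half-length 0.28, assurance 90% (Protocol 10.1).
- 16 completers per arm, 18 randomized per arm (Protocol 10.1).
- Two-arm parallel comparison with arm as the only effect (Protocol 10.3.2.2), so df = 2n − 2 for n per arm.

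**Formulas**

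- Log-scale SD: σ = √ln(1 + CV²) = √ln(1 + 0.49²) = 0.464.
- Half-length at the planning SD: H = t(0.95, df) × σ × √(2/n).
- Half-length not exceeded with 90% probability: H90 = H × √(χ²(0.90, df)/df).
- P(half-length ≤ 0.28) = chi-square distribution function with df degrees of freedom, evaluated at df × (0.28/H)².

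**Step 1: try to reproduce the plan's figure with 64 subjects (32 per arm, df = 62)**

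- H = 1.670 × 0.464 × 0.250 = 0.194.
- H90 = 0.194 × 1.112 = 0.215.
- P(≤ 0.28) is above 0.999.

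The inequality would be true, but 0.28 would be neither the expected nor the 90%-assured value, and the trial makes no such comparison.

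**Step 2: Part A completers (16 per arm, df = 30)**

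- H = 1.697 × 0.464 × 0.354 = 0.278.
- H90 = 0.278 × √(40.26/30) = 0.278 × 1.158 = 0.322.
- df × (0.28/H)² = 30.35, so P(≤ 0.28) = 0.552. A simulation of 200,000 trials gave 0.554.

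The plan's 0.28 therefore matches the half-length at the planning SD with 16 per arm and no allowance for assurance.

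**Step 3: other sample sizes, CV 49%**

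| Evaluable per arm | H | H90 | P(≤ 0.28) |
|---|---|---|---|
| 16 | 0.278 | 0.322 | 0.552 |
| 18 | 0.261 | 0.300 | 0.745 |
| 20 | 0.247 | 0.282 | 0.886 |
| 21 | 0.241 | 0.274 | 0.931 |
| 32 | 0.194 | 0.215 | > 0.999 |

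**Step 4: can another reading rescue the 90% at 16 per arm?**

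- Using 0.49 directly as the log SD: P = 0.39.
- Treating 0.28 as anything that rounds to it (below 0.285): P = 0.61.
- Pooling the variance over four arms (df = 60): P = 0.62.
- An 80% CI overshoots (P = 0.99), and the text says 90%.
- Working backwards, 16 per arm gives 90% only if the CV is about 42%. The plan states 49%.

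**Step 5: ratio scale, for a true ratio of 1**

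- At H: exp(±0.278) gives 0.76 to 1.32.
- At H90: exp(±0.322) gives 0.72 to 1.38.

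**The case against.** The strongest reply is that nothing operational depends on the figure. Part A is an estimation study. The plan sets no equivalence margin, PK hypothesis test or power claim, and no decision rule is tied to 0.28. The final report will show the actual interval, and the difference is 0.28 against 0.32 on the log scale. This stands as a limit on the consequences: no analysis result changes. It does not make the probability statement correct.

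Second, the CV quoted for Cmax is 23%. At that value, 16 per arm gives a half-length of 0.136 at the planning SD and 0.158 with 90% assurance, so 0.28 is met almost surely. This also stands. In practice the shortfall concerns the two AUC endpoints. The plan nevertheless applies 49% to all three parameters, so the sentence fails on its own terms.

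Third, the PK population is every dosed Part A subject with evaluable data, not completers only, and subjects may be replaced. With all 18 per arm evaluable, P rises to 0.745. The 55% is therefore the 16-completer case, but even the full randomized number falls short of 90%.

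Finally, 0.278 is the half-length when the observed SD equals the planning SD. The strict mean half-length is slightly lower, at 0.276. Both round to 0.28.

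**Conclusion.** The concern holds. With 32 Part A completers and a CV of 49%, the probability that the 90% CI half-length is at most 0.28 is about 55%, so the chance of missing the stated precision is about 45% rather than 10%. The half-length assured with 90% probability is about 0.32. The figure of 64 includes 32 subjects who contribute nothing to the ratio, and no reading with a 90% CI and a CV of 49% makes 0.28 the 90%-assured value, for 64 subjects or for 32.

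These figures assume log-normal PK parameters with equal variance in the two arms and 16 evaluable subjects in each. Because this is the sole sample-size justification, it must be corrected, though the correction changes neither the design nor the planned analysis.

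**What to change.** In Protocol 10.1 and SAP 7, replace the precision claim with wording such as: assuming a CV of 49%, 32 completers in Part A (16 per arm) give an expected 90% CI half-length of about 0.28 on the log scale; with 90% probability the half-length will not exceed about 0.32. Remove the 64 subjects from the PK precision claim. It would help to add that the half-length for Cmax should be shorter if its CV is near the 23% already quoted.

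The cost is two sentences across the two documents and a slightly less favourable stated figure. Enrolment, visits and the analysis model stay as they are. Keeping the 90% assurance at 0.28 would instead need about 21 evaluable subjects per arm in Part A (42 in total); that is not proposed here.
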